6.2.3 PRODUCT STORAGE AND STABILITY

Test Product:

Zip-stitch[™] clip storage: clips should be stored frozen (-10 to -30°C), as indicated on product labeling, in packaging. clips can be used up to the expiration date indicated on product labeling.

Zip-stitch[™] Applicator and loading tool storage: Applicator and loading tool should be stored at room temperature according to normal practices for reusable surgical instruments.

Reference Product:

VICRYL[™] storage: VICRYL[™] Sutures should be stored according to device labeling and standard hospital procedures.

Clinical monitoring will regularly ensure both test and reference devices are being stored as indicated.

6.2.4 DEVICE PREPARATION

Zip-stitch[™] clips are provided sterile and are ready for use. They should be opened by medical assistant during surgery into the sterile field as indicated in the device Instructions for Use. The Zip-stitch[™] reusable applicator and clip loading tools are not provided sterile and must be cleaned and sterilized before each procedure according to the device Instructions for Use provided.

During procedure, clips are to be loaded in the sterile field into applicator jaws using the clip loading tool. Once loaded, the device is ready for use in closing the vaginal cuff.

The reference device, VICRYL™ should be prepared according to device labeling and standard hospital procedures.

6.3 MEASURES TO MINIMIZE BIAS: RANDOMIZATION AND BLINDING

Variable block size randomization will be employed to assign a vaginal cuff closure method to each subject. At the time of enrollment and after confirmation of intraoperative eligibility, a subject will be randomly assigned treatment (cuff closure) with the test device (Zip-stitch™) or reference device (VICRYL™). This assignment will be provided via sponsor provided randomization envelopes broken down in 2:1 variable block sizes and stratified by site. Treatment allocation blocks will vary from three to six subjects and will be split 2:1 test to reference assignment. This method helps safeguard against a simple randomization generating a smaller than intended test or reference group.

Subjects will be blinded to the cuff closure method they receive during surgery. Because operating surgeons cannot be blinded to the treatment they are providing, this trial cannot be completely double-blinded. Every effort will be made to minimize bias in post-operative data collection. Data collection will be performed by an investigator without access to the blinded to treatment assignment. Treatment assignment will be recorded at the time of procedure in the electronic data capture system. After this point, the investigator collecting follow-up data will be blinded to medical records and treatment group. The operative surgeon cannot be blinded as the performed treatment. They will be available during follow-up as needed but will not participate in data collection for patients that they provided treatment.

Database lock and data un-blinding will take place after completion of the last six-week follow-up visit. Subjects will still participate in the 6 and 12-month visit and extension period call, but data will be unblinded. The data collected at the 12-month telephone visit are limited to pain, dyspareunia, and adverse events. Adverse events are likely to have significant clinical sequelae, and therefore not likely to be forgotten. Pain and dyspareunia are evaluated based on experience in the time frame of the call, and therefore are not affected by recall bias.

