Zip-Stitch[™] for Vaginal Cuff Closure in Laparoscopic Hysterectomy Safety & Efficacy Study

Protocol Number: QD-PRO-045 Rev 005

Principal Investigator: [name] M.D.

IDE Sponsor: ZSX Medical, LLC

Version Number: 5.0

6 March 2020

Summary of Changes from Previous Version:

Primary Affected Section(s)	Summary of Revisions Made	Rationale	
3.1	The primary study efficacy endpoint has been modified to evaluate the occurrence of implant passing events against a performance goal of 5% of patients. FDA requested that the primary endpoint be implant passing e without reference to associate safety/healing events.		
3.1	The primary safety endpoint has been modified to be evaluated through six weeks	FDA requested that dehiscence be valuated through six weeks for the primary endpoint.	
9	Statistical hypotheses have been eliminated. Study sample size rationale has been revised to reflect changes to the primary endpoint and performance goal.	FDA recommendation that comparison to 5% standard can be observational rather than statistical.	

The contents of this protocol are confidential and intended solely for the use of the investigator's team and the IRB/IEC. Do not copy or distribute contents of this document without written permission of ZSX Medical.

TABLE OF CONTENTS

S	TATE	EMENT OF COMPLIANCE	1
1		PROTOCOL SUMMARY	2
	1.1	Synopsis	2
	1.2	Schema	7
	1.3	Schedule of Activities (SoA)	
2		INTRODUCTION	
	2.1	Study Rationale	
	2.2	Background	
	2.3	Risk/Benefit Assessment	
		3.1 Known Potential Risks Associated with Laparoscopic hysterectomy	11
	2.3	3.2 Known Potential Risks Associated with the Use of Zip-stitch™ in	
	La	aparoscopic Hysterectomy	12

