4 STUDY DESIGN

4.1 OVERALL DESIGN

This randomized, controlled, blinded, prospective study will assess the safety and efficacy of the Zip-stitch™ Vaginal Cuff Closure System in achieving vaginal cuff closure following laparoscopic hysterectomy. This pivotal safety and efficacy study will begin at two sites and will be performed by a minimum of three surgeons but may be expanded to additional sites depending on enrollment. Additional sites may be inside or outside the United States.

The purpose of this trial is to evaluate the efficacy and safety of the Zip-stitch™ System. This will be accomplished by measure of the frequency of implant passing events and the frequency of postoperative vaginal cuff dehiscence, respectively. The observed rate of implant passing events will be numerically (not statistically) compared to a performance target of 5%.

A target of 59 women will be enrolled in a ratio of 2:1 test to reference (39 test and 20 reference subjects). This is based on a goal of 35 test subjects and an expected 10% of patients lost to follow-up. (See Section 9 for additional details).

During a pre-operative visit, a co-investigator surgeon may broach participation in this trial with candidate subjects. Potentially interested subjects will then be approached by a study coordinator or co-investigator surgeon other than their primary care provider to discuss study details and informed consent. Once obtained, surgery will be scheduled for interested participants.

Study enrollment will occur during surgery following satisfaction of all intra-operative exclusion criteria. This will take place after successful colpotomy, prior to initiation of vaginal cuff closure. Once enrolled, subjects will be randomized to receive cuff closure with either Zip-stitch™ or with VICRYL™ suture. Sealed randomization envelopes stratified by site and in variable block sizes will be provided in a blinded 2:1 ratio of test to reference cases. After randomization, the investigator surgeon will attempt to approximate and close the vaginal cuff using the assigned device. Integrity of the achieved closure will be visually assessed during each procedure, and laparoscopic video of cuff closure will be saved. Subjects will be blinded to the treatment they receive.

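### Section 6.3 discloses block sizes to unblinded operating surgeons and words the 2:1 split loosely; how predictable assignments become depends on how many earlier ones at the site a surgeon knows

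*Combined protocol and SAP*

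**What the plan says.** Section 6.3 describes assignment by "sponsor provided randomization envelopes broken down in 2:1 variable block sizes and stratified by site", and then gives the sizes: "Treatment allocation blocks will vary from three to six subjects and will be split 2:1 test to reference assignment". Section 4.1 adds that the envelopes are sealed: "Sealed randomization envelopes stratified by site and in variable block sizes will be provided in a blinded 2:1 ratio".

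The cover page describes the protocol as "intended solely for the use of the investigator's team and the IRB/IEC", a readership that includes the operating surgeons. Section 6.3 accepts that these surgeons know what they deliver: "Because operating surgeons cannot be blinded to the treatment they are providing, this trial cannot be completely double-blinded". Section 4.1 says the study "will begin at two sites and will be performed by a minimum of three surgeons".

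Eligibility is completed in theatre, after colpotomy and before cuff closure, and randomization follows at once (Sections 4.1 and 8.1). Part of that eligibility is surgeon judgment. Exclusion 19 in Section 5.2 turns on whether the surgeon finds adequate cuff tissue for laparoscopic suturing. Section 8.1 also lists, among the reasons for exclusion during surgery, the surgeon's own decision to close with suture and other complications.

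The documents do not say that block sizes are withheld from sites. They also do not give the mix of sizes in use, or how a block of four or five would be rounded.

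**The concern.** Varying the block size protects concealment to the extent that nobody at the site can tell where a block ends. Printing the sizes in the investigators' own document weakens that protection. For example, if a site's list opened with two reference assignments, the first block would have to be a six, because a block of three holds only one reference; the next four assignments would then all be test.

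The person who could use such knowledge is the one who decides, moments before the envelope is opened, whether the patient is enrolled. A surgeon who expects a clip could leave out a difficult cuff and enrol a similar patient when the next arm is less clear. That would unbalance the arms on prognosis. The test-versus-reference comparisons depend on its not happening, including the Fisher's exact comparison of dehiscence in Section 3.1.

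**Working it through.** **Inputs from the protocol.** Block range and 2:1 split (Section 6.3); site stratification and sealed envelopes (Sections 4.1 and 6.3); two starting sites and at least three surgeons (Section 4.1); the enrolment target: "A target of 59 women will be enrolled in a ratio of 2:1 test to reference (39 test and 20 reference subjects").

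**Assumptions not in the documents.** Blocks of three and six, equally likely. Thirty subjects per site (59/2 = 29.5). The surgeon knows all, a random half or a random third of the site's earlier assignments. Ranges below vary the share of threes from 0.3 to 0.7 and site size from 20 to 30.

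**1. The plan's own figure.** 35/(1 − 0.10) = 38.9, rounded up to 39 test; 39/2 = 19.5, rounded up to 20 reference; total 59. This reproduces the stated target.

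**2. Which sizes can be split 2:1.** The test count in a block of size b is 2b/3.
- b = 3: 2 test, 1 reference
- b = 4: 2.67 and 1.33, not possible
- b = 5: 3.33 and 1.67, not possible
- b = 6: 4 test, 2 reference

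Only three and six satisfy the sentence, so the sizes can be inferred from it.

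**3. Benchmark: fixed, known block size and full history.** An assignment is certain when every place left in the block belongs to one arm, so the expected number of certain assignments is the expected length of the last run in the block. With t test and r reference places, that is t/(r+1) + r/(t+1).
- Block of 3: 2/2 + 1/3 = 1.33; 1.33/3 = 44% certain
- Block of 6: 4/3 + 2/5 = 1.73; 1.73/6 = 29% certain

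**4. Varying blocks of three and six.** For an observer who knows the two sizes, let w be the current probability of each possible block state, with t test and r reference places left. Then P(next is test) = Σ w·t/(t+r). After each assignment the weights are updated by Bayes' rule. An assignment the surgeon did not see is averaged over both arms, and a completed block is followed by a new three or six with probability 1/2 each. Simulated site sequences of 30 give:

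| Earlier site assignments known | Best guess correct | Certain | Above 90% probability |
|---|---|---|---|
| All | about 75% | about 10% | about 31% |
| Half | about 68% | about 1% | about 7% |
| One third | about 67% | under 1% | about 3% |

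Always guessing test is right 66.7% of the time.

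**5. Sensitivity with full history.** Over the ranges above, correct guesses are 74–76%, certain assignments 6–12%, and assignments at 90% probability or more 22–36% (33% in the base case when exactly 90% is counted). Nearly all confident calls are for the test arm; only about 2% of assignments can be called as reference at 90% or more.

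**The case against.** The strongest reply is that full history is the extreme case. A surgeon necessarily learns only the assignments of her own patients. Sections 4.1, 4.2 and 6.3 give follow-up to an investigator who did not operate and has no access to the assignment, including through the electronic data capture system. With at least three surgeons over two sites, at least one site has two or more surgeons unless someone works at both. Full history therefore needs a site with a single operating surgeon, which the protocol permits but does not state, or leakage across the blind. This stands, and it is why the size of the effect must be given as a range.

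Other safeguards also count. Envelopes are sealed, consent precedes surgery, an intra-operative screening form is completed (Section 8.1), and screen-failure details are kept (Section 5.4), so selective exclusion would leave a trace. Three of the four numbered intra-operative exclusions are observable events. These measures limit or reveal abuse. They do not hide the next arm, and exclusion 19 and the decision to use suture remain discretionary.

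The consequence is limited too. The primary efficacy result is a numerical comparison of the passing rate with 5%, which Section 3.1 describes as non-comparative. The secondary comparisons are unpowered (Sections 4.2 and 9.2). The comparison with 5% is therefore less exposed, though not immune, because selective exclusion can change who enters the test arm. With 35 test subjects, one failure is 1/35 = 2.9% and two are 2/35 = 5.7%.

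Two stronger readings are tempting. A reader might infer that disclosure makes many assignments predictable at every site; the documents do not show that surgeons see every assignment, and with half the history known the gain is about one percentage point. A reader might also infer that the scheme cannot be carried out; Section 6.3 never says that blocks of four or five are used, and its range can mean three and six only.

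**Conclusion.** The point holds as an avoidable weakness in allocation concealment, together with one loosely worded sentence. It is a minor improvement, not a flaw that invalidates the randomization. Knowing the sizes raises the best-guess rate from 67% to between about 67% and 75%, and makes between under 1% and about 10% of assignments certain, depending on whether a surgeon knows one third or all of the site's earlier assignments. These figures rest on equal use of threes and sixes and 30 subjects per site, neither of which the documents state. The upper end applies to a site with one operating surgeon. The test-versus-reference comparisons are exposed most, and the numerical comparison with 5% less so.

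**What to change.** Replace the block-size sentence in Section 6.3 with wording such as: *Block sizes will vary at random and each block will be split 2:1; the sizes are held in a restricted randomization specification that is not available to sites.* List only multiples of three in that specification.

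Rewording cannot undo what sites have already read. For lists not yet issued, including those for any added site, re-draw the sequence from an undisclosed set of sizes that is not limited to three and six. Adding nines while keeping threes and sixes helps only modestly if the mix becomes known: with full history the best guess falls from about 75% to 73%, and certain assignments from about 10% to 4%. Withholding the new set therefore matters as much as changing it.

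The cost is one protocol sentence, a short restricted document and a re-drawn envelope set where envelopes are still unissued. The downside is slightly looser 2:1 balance within a site. The change does nothing for envelopes already issued, and the documents do not say whether any have been.

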1.1 SYNOPSIS

Zip-Stitch[™] for Vaginal Cuff Closure in Laparoscopic Hysterectomy - Safety

& Efficacy Study

IDE Number: G190106/A001

Sponsor: ZSX Medical LLC

[name]

Study Description:This is a prospective, blinded, randomized, controlled study to assess the

safety and efficacy of the Zip-stitch™ System in maintaining vaginal cuff closure following laparoscopic hysterectomy. Participating subjects will be randomized and evaluated for implant passing, successful cuff closure, healing, adverse events, dyspareunia, and pain. Blinded follow-up will involve in-person visits at one week, six weeks, and six months. There will be an additional unblinded follow-up by telephone at 12 months post

operatively.

Objectives: Primary Objective: The primary objective of this study is to evaluate the

efficacy and safety of the Zip-stitch™ Vaginal Cuff Closure system. This will be accomplished by determining the frequency of spontaneous implant passing events and frequency of postoperative vaginal cuff dehiscence, respectively. Primary reporting of both endpoints will take place at six

weeks postoperative.

Secondary Objectives: The secondary objective of this study is to demonstrate the safety and efficacy of the Zip-stitch[™] System as compared to a reference treatment (VICRYL[™]). This will be evaluated by assessing cuff closure and healing, adverse events, changes between pre-operative

and post-operative pain and dyspareunia, and implant passing.

Endpoints: Primary Endpoints:

Efficacy: The primary efficacy endpoint for this study is frequency of implant passing following cuff closure. This will be evaluated through six-

weeks post-operative.

Safety: The primary safety endpoint in this study is frequency of vaginal cuff dehiscence. This will be evaluated through six-weeks post-operative.

Secondary Endpoints (Exploratory):

(1) Binary assessment of cuff closure one, six weeks, and six months after surgery (test versus reference group) based on surgeon

evaluation.

- (2) Binary assessment of cuff healing six weeks and six months after surgery (test versus reference group) based on surgeon evaluation.
- (3) Comparison of implant passing. Percentage of subjects experiencing implant passing will be compared between test and control groups as of the six-week and six-month visits.

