- 8. Evidence of pelvic inflammatory disease (PID)
- 9. Known clotting defects or bleeding disorders
- 10. Hemoglobin < 8 g/dL
- 11. Metastatic disease
- 12. On anticoagulant therapy
- 13. Participation in another interventional trial
- 14. Pregnancy
- 15. Abnormal PAP results that have not been fully evaluated, or in the opinion of the investigator may indicate risk of abnormal vaginal cuff healing
- 16. Co-morbidities that, in the opinion of the investigator, may indicate risk of abnormal vaginal cuff healing

Intra-operative Exclusion Criteria

- 17. Bowel injury during laparoscopic hysterectomy procedure prior to attempted cuff closure
- 18. Bladder injury during laparoscopic hysterectomy procedure prior to attempted cuff closure
- 19. Cases in which surgeon cannot identify adequate tissue along the cuff to apply suture laparoscopically
- 20. Cases requiring conversion to laparotomy prior to study intervention

Description of Sites/Facilities Enrolling Participants:

The primary sites in this study will be:

Thomas Jefferson University Hospital with locations at [name] and [name]; and

Hershey Medical Center, Penn State College of Medicine at [name].

Enrollment may take place at any of these locations.

There may be additional sites within or outside the United States added (but not more than three total institutions), based upon enrollment.

Description of Study Intervention:

The Zip-stitch™ Vaginal Cuff Closure System is a surgical wound closure system consisting of a series of clips and a reusable, re-sterilizable clip applicator. The clips are made of the bio-absorbable polymer poly-p-dioxanone (PDO) and maintain closure of the vaginal cuff during the healing process, then are ultimately absorbed by the body five to eight months after application.

Protocol QD-PRO-045 Rev 005

Indication for Use:

The Zip-stitch™ System's indication for use is to close the vaginal cuff

following laparoscopic hysterectomy.

Study Duration: Enrollment is intended to occur over three to five months and follow-up is

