12-months long. Consequently, this study is expected to take a total of 15 to 17 months from beginning of enrollment to completion of follow-up. Additionally, study blinding will be removed after the last subject completes their six-week follow-up timepoint, and 6 and 12-month follow-up will be collected unblinded. Data will be submitted for regulatory

study follow-up after 6 and 12 months.

Participant Duration: Intervention will occur at the time of surgery and subjects will complete a

12-month follow-up program, including in-person visits at one week, six weeks, and six months, as well as a telephone follow-up at 12-months.

review following unblinding at six weeks, and again after completion of

Statistical Methods: Analysis Populations:

Intent-to-treat population (ITT): This population will include all subjects enrolled and randomized to test or reference treatment. Subjects will be analyzed according to the treatment to which they were randomized,

regardless of the treatment they actually received.

Safety population: This population will include all subjects enrolled and randomized to test or reference treatment. Subjects will be analyzed according to the treatment that they received; patients randomized to the reference arm that receive Zip-stitch™ will be included in the Zip-stitch™ safety population. Similarly, patients randomized to the Zip-stitch™ arm that receive sutures will be included in the reference safety population.

Primary and secondary efficacy endpoint analyses will be performed on the ITT population. All safety analyses will be performed on the Safety population.

Efficacy Analysis:

Unless otherwise stated the analyses of efficacy endpoints will be based on the ITT population as follows.

One-sided endpoint analyses will be performed with 80% statistical power; corresponding *p*-values will be reported, and all two-sided analyses and comparisons between groups will be performed assuming a 0.05 significance level. The corresponding *p*-values and 95% confidence intervals (CIs) will be reported.

Primary Efficacy Endpoint:

Frequency of spontaneous implant passing events will be reported through six weeks. Event frequency will be numerically compared to a performance target of 5%.

Secondary Efficacy Endpoints:

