3 OBJECTIVES AND ENDPOINTS

The primary objectives of this study are to evaluate the efficacy and safety of the Zip-stitch™ Vaginal Cuff Closure System. These will be evaluated by measuring the frequency of implant passing events and frequency of postoperative vaginal cuff dehiscence, respectively.

Additionally, this study aims to further assess and characterize the safety and efficacy of the Zip-stitch[™] System as compared to a reference treatment (VICRYL[™] suture) through secondary endpoints. These include analysis of cuff closure and healing, adverse events, changes between pre-operative and post-operative pain and dyspareunia, and implant passing.

Data through six months may be used to support market clearance of the device by FDA.

OBJECTIVES	ENDPOINTS	JUSTIFICATION FOR ENDPOINTS	
Primary			
The primary objective of this study is to evaluate the efficacy and safety of the Zip-stitch™ Vaginal Cuff Closure System. This will be accomplished by measuring the frequency of implant passing events and frequency of postoperative vaginal cuff dehiscence, respectively.	(Efficacy) The primary efficacy endpoint for this study is frequency of implant passing events (as defined in this protocol), evaluated through six-weeks post-operative. (Safety) The primary safety endpoint in this study is frequency of vaginal cuff dehiscence, evaluated through six-weeks post-operative.	(Efficacy) FDA has expressed interest in determining the frequency of implant passing as a surrogate for Zip-stitch™ function. (Safety) FDA has recognized vaginal cuff dehiscence as an important safety metric for cuff closure.	
Secondary			
The secondary objective of this study is to demonstrate the safety and efficacy of the Zip-stitch™	(1) Binary assessment of cuff closure one, six weeks, and six months after surgery (test versus reference group) based on surgeon evaluation.	(1) Comparison of cuff closure up to six months after surgery provides a fundamental evaluation of test and reference device efficacy.	

OBJECTIVES	ENDPOINTS	JUSTIFICATION FOR ENDPOINTS		

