3.1 PRIMARY ENDPOINT

(Efficacy) Frequency of Implant Passing Events

Frequency of implant passing events will be reported for all subjects. Failure in this endpoint is defined, on a per patient basis, as the presence of one or more spontaneous implant passing events. A single event may be one or more clips or sutures being spontaneously passed by the patient (*i.e.*, not removed by medical staff).

Frequency of implant passing (either clips or sutures) will be explicitly collected at each follow-up visit; however, events may be reported between visits or during unexpected visits. When implant passing is reported, subjects will be asked to collect and provide passed implants, and an in-person evaluation will be performed. This will involve a visual cuff closure and healing assessment.

In the final analysis of this primary efficacy analysis, the rate of implant passage will be reported through six weeks. The primary objective of this endpoint is to observe a study population failure rate of less than 5% and is neither statistically-driven nor comparative.

(Safety) Frequency of Vaginal Cuff Dehiscence

Vaginal cuff dehiscence is defined as rupture of the surgical wound requiring surgical re-intervention. The proportion of subjects who experience vaginal cuff dehiscence up to six weeks after surgery will be evaluated. In the final analysis of this primary safety endpoint, failure will be reported, and test and control groups will be compared using Fisher's exact test to assess for a possible difference between groups.

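### The protocol gives conflicting times for breaking the blind and never says who is unblinded, which may expose the exploratory six-month comparisons, mainly pain and dyspareunia, to knowledge of treatment

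*Combined protocol and SAP*

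**What the plan says.** Two different times for breaking the blind stand in the current text.

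- **After the last six-week visit.** Section 6.3: "Database lock and data un-blinding will take place after completion of the last six-week follow-up visit". The synopsis (1.1, study duration) says that "study blinding will be removed after the last subject completes their six-week follow-up timepoint" and that "6 and 12-month follow-up will be collected unblinded". Section 4.2 also unblinds the data after six-week follow-up.
- **After six months.** The synopsis (1.1, study description): "Blinded follow-up will involve in-person visits at one week, six weeks, and six months", followed by "There will be an additional unblinded follow-up by telephone at 12 months post" (the sentence ends with the word for after surgery). Section 8.1, under the six-month visit, unblinds the data only when all six-month visits are complete.

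On who is masked, sections 4.1 and 6.3 describe the subjects and the follow-up investigator as blinded and give no end date. Sections 4.2, 6.3 and 8.1 speak of unblinding data, while the synopsis speaks of study blinding as a whole. For the six-month visit, section 8.1 requires only that the data collector is not the person who closed the cuff.

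Section 3 adds: "Data through six months may be used to support market clearance of the device by FDA".

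**The concern.** The rules cannot all be followed, and two sites could act differently in good faith. One might tell subjects their assignment, or open it to the assessor, once six-week follow-up closes; another might hold the blind to six months.

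The justification in 4.2 and 6.3 for collecting later data unblinded deals with recall bias. Knowledge of treatment is a different source of bias, and neither section addresses it. Section 4.2 also points out that 12-month data are not compared statistically, but that does not cover six months, where most of the secondary comparisons fall.

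Dyspareunia and pain (endpoints 6 and 7) would be most exposed if subjects were told, because they are self-reported and their only between-group test is at six months. Section 2.3.2 itself raises the possibility that the clip contributes to dyspareunia while it degrades, so a subject's belief about her device could plausibly influence her answers. Closure and healing at six months (endpoints 1 and 2) would be exposed if assessors were unmasked. Implant passing and adverse events (3 and 5) would be exposed only for events after code break.

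**Working it through.** **1. The sections side by side**

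| Section | Blind ends | Who is covered |
|---|---|---|
| 1.1 study description | Six-month visit blinded; only the 12-month call unblinded | Not stated |
| 1.1 study duration | After last six-week visit | Study blinding in general; six-month collection is unblinded |
| 4.1 | No end date | Subjects and follow-up co-investigator are blinded |
| 4.2 | After six-week follow-up | Data |
| 6.3 | After last six-week visit | Data; subjects and follow-up investigator blinded, no end date |
| 8.1 | After all six-month visits | Data |

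The synopsis disagrees with itself, and the procedures section disagrees with the blinding section. Read literally, 8.1 would also block the six-week report by group that 3.1 and 9.4.7 call for.

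**2. What is compared at six months (9.4.4 and 9.4.5)**

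Two-sided Fisher's exact tests are planned for closure (1), healing (2) and implant passing (3) at six weeks and six months (closure also at one week), adverse events by six months (5), and dyspareunia (6) and pain (7) from baseline to six months only. Endpoint 4 stops at six weeks. So six of seven are compared at or by six months. The list in 4.2 of what is collected at six and 12 months omits closure, healing and implant passing, although 8.1 collects all three at six months. That is a related wording error.

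**3. How many six-month visits would follow code break under the six-week rule**

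Inputs from the protocol:
- enrolment T = 3 to 5 months (1.1)
- six-week visit at 42 ± 5 days, six-month visit ± 7 days (8.1)
- target of 59 subjects (1.1), which reproduces: 35/0.9 = 38.9, so 39 test; 39/2 = 19.5, so 20 reference; 39 + 20 = 59

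Assumptions: a month is 30.4375 days; accrual is uniform; any delay L between the last six-week visit and lock is assumed.

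42 days = 1.380 months. The least favourable windows are the last six-week visit 5 days late and six-month visits 7 days early, so W = 12 days = 0.394 months. A 30-day lock delay is L = 0.986 months.

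Share after code break = 1 − max(0, (T + 1.380 + L + W − 6)/T)

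| Case | T = 3 | T = 4 | T = 5 |
|---|---|---|---|
| Nominal days, no lag | 100% | 100% | 1 − 0.380/5 = 92.4% |
| Worst windows, no lag | 100% | 100% | 1 − 0.774/5 = 84.5% |
| 30-day lag | 100% | 90.9% | 72.7% |
| 30-day lag and worst windows | 100% | 81.0% | 64.8% |

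At five months without lag this is 0.924 × 59 = 54.5, or 0.845 × 59 = 49.9 with the worst windows. With the protocol's expected 10% loss (59 × 0.9 = 53.1, about 53 attending) the counts are about 49 and 45.

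If accrual declines linearly, the share is squared. With the 30-day lag and worst windows it becomes 0.810² = 65.6% (T = 4) and 0.648² = 42.0% (T = 5).

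With nominal days and no lag, a six-month visit can precede code break only if enrolment exceeds 6 − 1.380 = 4.62 months. Beyond that the share is 4.62/T, so an overrun to an assumed 9 or 12 months would give 51% or 38.5%.

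**The case against.** The best defence is that unblinding the data means releasing codes to analysts, while subjects and assessors stay masked. Sections 4.2 and 6.3 permit that reading, and no section says that subjects are told. The six-week rule appears three times and serves a stated purpose, reporting the primary endpoints, so the two conflicting statements may be leftover text. The one in 8.1 might mean only the six-month data. The stakes are also limited. Sections 4.1 and 9.4.7 make the six-week report the final one and later data supplementary. The secondary endpoints are exploratory and unpowered, and endpoints 1 to 3 also have six-week comparisons made under the blind.

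Part of this stands. If only analysts are unblinded, little bias follows, and the singling out of pain and dyspareunia depends on subjects being told. The share of exposed visits depends on enrolment length, lag and attrition.

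It does not settle the matter. The synopsis says six-month follow-up is itself gathered unblinded, and that happens at the visit, not in the analysis. Calling the other statements leftover text is a guess, and they still need correcting. Endpoints 1, 2, 3, 6 and 7 carry six-month acceptance criteria, and section 3 foresees regulatory use of six-month data, so whether those data were masked has to be clear.

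**Conclusion.** The contradiction is certain and should be fixed. The bias is conditional: it arises only if the six-week rule is applied to subjects or assessors, which the text neither states nor excludes. If it is, most or all six-month visits would follow code break under the planned enrolment: 92% to 100% with nominal days, and 85% to 100% with the least favourable windows. Both ranges assume uniform accrual and no lock delay. Delay, front-loaded accrual or a longer enrolment period would lower them. The primary endpoints are safe, because every version keeps the blind until the last six-week visit.

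**What to change.** Bring the synopsis (study description and study duration), 4.1, 4.2, 6.3 and 8.1 to one rule that treats analysts separately from subjects and assessors:

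- At the six-week lock, release codes only to the sponsor and statistical staff who prepare the primary report.
- Keep subjects and follow-up assessors masked until all six-month visits are complete, using the access restriction already in 4.2 and 6.3.
- Reword 8.1 so that its unblinding statement covers subjects and assessors and does not block the six-week report.
- Correct the list of six-month data in 4.2.
- State a limitation. Assessors who see clips or suture on inspection (3.3) may be unmasked whatever the code-release rule. So may subjects who pass an implant, since 3.1 says "subjects will be asked to collect and provide passed implants, and an in-person evaluation will be performed".

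If the sponsor prefers full unblinding at six weeks, every section should say so and the six-month comparisons should be labelled unblinded.

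The cost is wording, plus keeping an existing restriction in force longer. Operating surgeons and the data capture system already hold assignments. Subjects would learn theirs about 6 − 1.380 = 4.62 months later than under the six-week rule, and staff who hold codes must be kept away from assessors and subjects. The six-week report is not delayed.
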